Appendix 2: Protocol Amendment History

Version Date	Description of Change	Brief Rationale
V25 February 2023	Title page, Statement of Compliance: Updated to add NIH as a funding source and to require following the terms and conditions of the award 11.1.3: Added language regarding a Certificate of Confidentiality 11.3: Added language regarding abiding by the NIH Public Access Policy	The study has received an NIH R21 grant to fund the study
	8.2.5: Added a sentence excluding the DRS from baseline	The decision that is of interest hasn't occurred yet at baseline
	1.2 Schema: Changed "14" to "1 - 90" days after surgery or radiation for adjuvant endocrine therapy	Internal consistency
V24 June 2022	Revised TOC and made formatting changes	To correct TOC and formatting
	In Section 6.6, removed language indicating the concomitant medications need to be recorded in the case report forms	To reduce study team burden by reducing extraneous information collection
V23 March 2022	In the study calendar, revised the follow-up Visit 1 to broaden the window from 60 days +/- 30 days to any time 1-90 days past surgery, chemotherapy completion, or RT completion, whichever is later.	To align with clinical practice
V26 January 2022	Updated TOC and made formatting revisions	To correct formatting
	Changed the title of the study from "A Pilot Study of Neoadjuvant Endocrine Therapy Tolerance to Inform Treatment Decisions for Adjuvant Radiation in Geriatric, Early Stage ER+ Breast Cancer" to "Pre-Operative Window of Adjuvant Endocrine Therapy to Inform Radiation Therapy Decisions in Older Women with Early-Stage Breast Cancer." Changed the Study ID from "Breast 52" to "POWER"	To differentiate this study from a different study with a similar title, and to give the study a more recognizable ID.
	Added information to include sites external to UVA. This includes additional reporting requirements, addition of information for VCU, and addition of information regarding the MCRO	To expand this study in allowing additional sites to participate in this clinical trial

Pre-Operative Window of Adjuvant Endocrine Therapy to Inform Radiation Therapy Decisions in Older Women with Early-Stage Breast Cancer

Version Date: 21 February 2023

	Replaced “neoadjuvant” with “pre-operative endocrine therapy (pre-ET)” in most places when referencing this study therapy	For clarity
	Added language to the first secondary endpoint	Clarity
	Added a secondary endpoint to include assessment of the effect of pre-ET on decisional outcomes for adjuvant therapy after BCS	To expand the study endpoints/objectives
	Removed UVA-specific language from Section 5.6 regarding process for recruitment.	To allow external site(s) to follow their established procedures
	Clarified that radiation oncologists should see subjects on or at Day 1 to answer the radiation preference questions, and that the questions should be answered at Day 1 and at the pre-operative visit.	Clarity
	Added the Decisional Conflict Scales and Decision Regret Scale to the study, including in the calendar and appendices	To assess subjects' perceptions related to their medical decisions
	Added a Treatment Decision Survey at Day 1 of adjuvant therapy and added this survey to the appendix	To assess why participants made decisions about their treatment
	Removed the mild, moderate, and severe grading guidelines in section 9.1.3.1	AEs should be graded according to the CTCAE. Events that do not have their own term should be graded with the “other” category
	In Section 10.2, clarified that the pre-op and on-study responses measuring change in preference can be no to yes or yes to no	Clarity
	In the study calendar, lengthened the window for Visit 1 in the adjuvant treatment period and clarified the timeframe for this visit relative to chemotherapy completion	For clarity, and to make the calendar easier to follow
	In the study calendar, clarified with a footnote that after the day 90 visit, participants may continue the pre-operative endocrine therapy until 2-8 weeks before surgery based on clinician discretion and SOC. Clarified that the surgery should occur 2-8 weeks after Day 90. Fixed a footnote at Rad Onc RT preference day 1 (changed from “i” to “h”). Clarified footnote “h” to specify that the footnote applies to the questionnaires. Added footnote “j” to Surgery visit to clarify that participants should be off of	For clarity and correctness.

Pre-Operative Window of Adjuvant Endocrine Therapy to Inform Radiation Therapy Decisions in Older Women with Early-Stage Breast Cancer

Version Date: 21 February 2023

	endocrine therapy for at least 2 weeks and no longer than 8 weeks prior to surgery.	
	In the study calendar, expanded the visit timeframe windows to 30 days for adjuvant treatment visits 2, 3, and 4	To reduce unnecessary restrictions
V27 January 2021	Updated TOC	To reflect shifted page numbers
	Formatting revisions throughout document	To correct formatting
	Updated the title sheet with the NCT number	To update NCT information
	In Sections 1, 2 and 5, updated the Prime II data and changed age inclusion criteria from females \geq 70 to females \geq 65	To reflect updated data presented from the PRIME II trial which includes patients ages 65 and above
	In Sections 6.5, 8.2.2, 10, and 13, revised the schedule of the radiation preference questions to occur at the pre-op visit instead of the post-op visit	To increase compliance with this study procedure
	In Section 11.1.2, added that consent may occur via Telemedicine	To allow for the use of telemedicine
	In Appendix 1 Schedule of Events, added physical exam/vitals to the Pre-Op Visit	Physical exam/vitals are part of the pre-op visit (standard of care)
	In Appendix 1 Schedule of Events and schema, removed the Post-Op visit	Visit is not needed, as no study procedures are performed at the Post-Op visit
	In Section 13 (Appendix 10), updated the adherence questions	To update the adherence questions
V18 March 2020	Listed additional radiation oncologist sub-investigators on the coverpage.	To address secondary endpoint regarding radiation oncologist RT therapy preference
	Updated TOC.	To address use of CESD-R and sections shifted with described revisions
	CESD-R added in abbreviations, section 4.1, 8.2.3 and appendix 8.	To replace the HADS for assessment of depression
	Added details regarding radiation oncologist RT preference questions in synopsis, section 3, 6.5, 8.2.2 and appendix 1.	To address secondary endpoint regarding radiation oncologist RT therapy preference
	Added pre-operative visit and footnotes in appendix 1	To address AE assessment prior to surgery and RT preference questions window
	Added "not applicable" response option in appendix 10 question 1 regarding how often subjects take ET.	For day 1 of pre-ET and visit 1 of adjuvant ET
	Reformatted surveys in appendix 3, 4, 5, and 6.	To improve readability and mimic participant surveys.

Pre-Operative Window of Adjuvant Endocrine Therapy to Inform Radiation Therapy Decisions in Older Women with Early-Stage Breast Cancer

Version Date: 21 February 2023

V04 November 2019	Table 1 (recording guidelines for high-risk studies) was revised to include recording guidelines for medium risk studies. Updated page numbers in TOC	The PRC reviewed this study and determined the study meets the criteria for a medium risk study.
	Formatting revisions throughout document	Formatting corrections
	Updated page numbers in TOC	Sections shifted with described revisions

Appendix 3: The Brief Illness Perception Questionnaire (BIP-Q)

For the following questions, please circle the number that best corresponds to your views:

How much does your illness affect your life?												
No affect at all	0	1	2	3	4	5	6	7	8	9	10	Severely affects my life
How long do you think your illness will continue?												
A very short time	0	1	2	3	4	5	6	7	8	9	10	Forever
How much control do you feel you have over your illness?												
Absolutely no control	0	1	2	3	4	5	6	7	8	9	10	Extreme amount of control
How much do you think your treatment can help your illness?												
Not at all	0	1	2	3	4	5	6	7	8	9	10	Extremely helpful
How much do you experience symptoms from your illness?												

Pre-Operative Window of Adjuvant Endocrine Therapy to Inform Radiation Therapy Decisions in Older Women with Early-Stage Breast Cancer

Version Date: 21 February 2023

No symptoms at all	0	1	2	3	4	5	6	7	8	9	10	Many severe symptoms
How concerned are you about your illness?												
Not at all concerned	0	1	2	3	4	5	6	7	8	9	10	Extremely concerned
How well do you feel you understand your illness?												
Don't understand at all	0	1	2	3	4	5	6	7	8	9	10	Understand very clearly
How much does your illness affect you emotionally (e.g. does it make you angry, scared, upset or depressed)?												
Not at all affected emotionally	0	1	2	3	4	5	6	7	8	9	10	Extremely affected emotionally
Please list in rank-order the three most important factors that you believe caused your illness. The most important causes for me:												
1.												
2.												
3.												

Pre-Operative Window of Adjuvant Endocrine Therapy to Inform Radiation Therapy Decisions in Older Women with Early-Stage Breast Cancer

Version Date: 21 February 2023

Appendix 4: Beliefs about Medicines Questionnaire

General:

For the following questions, please circle the number that best corresponds to your views:

1. Doctors use too many medicines.				
1 Strongly Disagree	2 Disagree	3 Uncertain	4 Agree	5 Strongly Agree
2. People who take medicines should stop their treatment for a while every now and again.				
1 Strongly Disagree	2 Disagree	3 Uncertain	4 Agree	5 Strongly Agree
3. Most medicines are addictive.				
1 Strongly Disagree	2 Disagree	3 Uncertain	4 Agree	5 Strongly Agree
4. Natural remedies are safer than medicines.				

Pre-Operative Window of Adjuvant Endocrine Therapy to Inform Radiation Therapy Decisions in Older Women with Early-Stage Breast Cancer

Version Date: 21 February 2023

1 Strongly Disagree	2 Disagree	3 Uncertain	4 Agree	5 Strongly Agree
5. Medicines do more harm than good.				
1 Strongly Disagree	2 Disagree	3 Uncertain	4 Agree	5 Strongly Agree
6. All medicines are poisons.				
1 Strongly Disagree	2 Disagree	3 Uncertain	4 Agree	5 Strongly Agree
7. Doctors place too much trust on medicines.				
1 Strongly Disagree	2 Disagree	3 Uncertain	4 Agree	5 Strongly Agree
8. If doctors had more time with patients, they would prescribe fewer medicines.				
1 Strongly Disagree	2 Disagree	3 Uncertain	4 Agree	5 Strongly Agree

Endocrine Therapy:

Brett J et al. Psychometric properties of the Beliefs about Medicine Questionnaire-adjuvant endocrine therapy (BMQ-AET) for women taking AETs following early-stage breast cancer. Health Psychol Open 2017:1-8

9. My health depends on my hormone treatment.				
1 Strongly Disagree	2 Disagree	3 Uncertain	4 Agree	5 Strongly Agree
10. My life will be impossible without my hormone treatment.				
1 Strongly Disagree	2 Disagree	3 Uncertain	4 Agree	5 Strongly Agree
11. Without my hormone treatment I will be very ill.				

Pre-Operative Window of Adjuvant Endocrine Therapy to Inform Radiation Therapy Decisions in Older Women with Early-Stage Breast Cancer

Version Date: 21 February 2023

1 Strongly Disagree	2 Disagree	3 Uncertain	4 Agree	5 Strongly Agree
12. My health in the future will depend on my hormone treatment.				
1 Strongly Disagree	2 Disagree	3 Uncertain	4 Agree	5 Strongly Agree
13. Having to use my hormone treatment worries me.				
1 Strongly Disagree	2 Disagree	3 Uncertain	4 Agree	5 Strongly Agree
14. I sometimes worry about the long-term side effects of my hormone treatment.				
1 Strongly Disagree	2 Disagree	3 Uncertain	4 Agree	5 Strongly Agree
15. My hormone treatment is a mystery to me.				
1 Strongly Disagree	2 Disagree	3 Uncertain	4 Agree	5 Strongly Agree
16. My hormone treatment will disrupt my life.				
1 Strongly Disagree	2 Disagree	3 Uncertain	4 Agree	5 Strongly Agree
17. I sometimes worry about becoming too dependent on my hormone treatment.				
1 Strongly Disagree	2 Disagree	3 Uncertain	4 Agree	5 Strongly Agree
18. My hormone treatment protects me from getting worse.				
1 Strongly Disagree	2 Disagree	3 Uncertain	4 Agree	5 Strongly Agree

Pre-Operative Window of Adjuvant Endocrine Therapy to Inform Radiation Therapy Decisions in Older Women with Early-Stage Breast Cancer

Version Date: 21 February 2023

Appendix 5: Perceived Sensitivity to Medicine Scale

1. My body is very sensitive to medicines.				
1 Strongly Disagree	2 Disagree	3 Uncertain	4 Agree	5 Strongly Agree
2. My body overreacts to medicines.				
1 Strongly Disagree	2 Disagree	3 Uncertain	4 Agree	5 Strongly Agree
3. I usually have stronger reactions to medicines than most people.				
1 Strongly Disagree	2 Disagree	3 Uncertain	4 Agree	5 Strongly Agree
4. I have had a bad reaction to medicines in the past.				
1 Strongly Disagree	2 Disagree	3 Uncertain	4 Agree	5 Strongly Agree
5. Even very small amounts of medicines can upset my body.				

Pre-Operative Window of Adjuvant Endocrine Therapy to Inform Radiation Therapy Decisions in Older Women with Early-Stage Breast Cancer

Version Date: 21 February 2023

1 Strongly Disagree	2 Disagree	3 Uncertain	4 Agree	5 Strongly Agree
---------------------------	---------------	----------------	------------	---------------------

For the following questions, please circle the number that best corresponds to your views:

Pre-Operative Window of Adjuvant Endocrine Therapy to Inform Radiation Therapy Decisions in Older Women with Early-Stage Breast Cancer

Version Date: 21 February 2023

Appendix 6: UVA Breast Cancer Belief Survey

For the following questions, please circle the number that best corresponds to your views:

1. I worry a lot about a return of breast cancer at some point in my life.				
1 Strongly Disagree	2 Disagree	3 Agree	4 Strongly Agree	
2. Getting breast cancer again would be devastating to me.				
1 Strongly Disagree	2 Disagree	3 Agree	4 Strongly Agree	
3. The side effects of a medicine prescribed by my doctor are important when I consider if I will continue taking the medicine.				
1 Strongly Disagree	2 Disagree	3 Agree	4 Strongly Agree	
4. If I know a medication can help lower my risk of getting breast cancer again, I will continue to take it even if I have side effects.				
1 Strongly Disagree	2 Disagree	3 Agree	4 Strongly Agree	
Most medicines prescribed by your doctor can have side effects. Sometimes these side effects are very minor and sometimes they can be severe. Thinking about the medicine that will be prescribed for your cancer please consider how the side effect would impact you taking the medicine.				
For each possible side effect please circle whether you would stop for mild, moderate, or severe symptoms or whether you would not stop at all.				
Joint pains, general aches, muscle stiffness...	Mild	Moderate	Severe	I would not stop
Vaginal dryness, pain with intercourse, difficulty with bladder control...	Mild	Moderate	Severe	I would not stop

Pre-Operative Window of Adjuvant Endocrine Therapy to Inform Radiation Therapy Decisions in Older Women with Early-Stage Breast Cancer

Version Date: 21 February 2023

Weight gain, unhappy with appearance of my body...	Mild	Moderate	Severe	I would not stop
Difficulty concentrating, forgetfulness, easily distracted...	Mild	Moderate	Severe	I would not stop
Nausea, vomiting...	Mild	Moderate	Severe	I would not stop

Pre-Operative Window of Adjuvant Endocrine Therapy to Inform Radiation Therapy Decisions in Older Women with Early-Stage Breast Cancer

Version Date: 21 February 2023

Appendix 7: EORTC QLQ

EORTC QLQ-C30 (version 3)

[figure not shown]
We are interested in some things about you and your health. Please answer all of the questions yourself by circling the number that best applies to you. There are no "right" or "wrong" answers. The information that you provide will remain strictly confidential.

Please fill in your initials:

Your birthdate (Day, Month, Year):

Today's date (Day, Month, Year):

31

1. Do you have any trouble doing strenuous activities, like carrying a heavy shopping bag or a suitcase?
2. Do you have any trouble taking a long walk?
3. Do you have any trouble taking a short walk outside of the house?
4. Do you need to stay in bed or a chair during the day?
5. Do you need help with eating, dressing, washing yourself or using the toilet?

	Not at All	A Little	Quite a Bit	Very Much
1	1	2	3	4
2	1	2	3	4
3	1	2	3	4
4	1	2	3	4
5	1	2	3	4

During the past week:

6. Were you limited in doing either your work or other daily activities?
7. Were you limited in pursuing your hobbies or other leisure time activities?
8. Were you short of breath?
9. Have you had pain?
10. Did you need to rest?
11. Have you had trouble sleeping?
12. Have you felt weak?
13. Have you lacked appetite?
14. Have you felt nauseated?
15. Have you vomited?
16. Have you been constipated?

	Not at All	A Little	Quite a Bit	Very Much
6	1	2	3	4
7	1	2	3	4
8	1	2	3	4
9	1	2	3	4
10	1	2	3	4
11	1	2	3	4
12	1	2	3	4
13	1	2	3	4
14	1	2	3	4
15	1	2	3	4
16	1	2	3	4

Please go on to the next page

Pre-Operative Window of Adjuvant Endocrine Therapy to Inform Radiation Therapy Decisions in Older Women with Early-Stage Breast Cancer

Version Date: 21 February 2023

During the past week:

During the past week:	Not at All	A Little	Quite a Bit	Very Much
17. Have you had diarrhea?	1	2	3	4
18. Were you tired?	1	2	3	4
19. Did pain interfere with your daily activities?	1	2	3	4
20. Have you had difficulty in concentrating on things, like reading a newspaper or watching television?	1	2	3	4
21. Did you feel tense?	1	2	3	4
22. Did you worry?	1	2	3	4
23. Did you feel irritable?	1	2	3	4
24. Did you feel depressed?	1	2	3	4
25. Have you had difficulty remembering things?	1	2	3	4
26. Has your physical condition or medical treatment interfered with your family life?	1	2	3	4
27. Has your physical condition or medical treatment interfered with your social activities?	1	2	3	4
28. Has your physical condition or medical treatment caused you financial difficulties?	1	2	3	4

For the following questions please circle the number between 1 and 7 that best applies to you

29. How would you rate your overall health during the past week?

1 2 3 4 5 6 7
Very poor Excellent

30. How would you rate your overall quality of life during the past week?

1	2	3	4	5	6	7
Very poor				Excellent		

Pre-Operative Window of Adjuvant Endocrine Therapy to Inform Radiation Therapy Decisions in Older Women with Early-Stage Breast Cancer

Version Date: 21 February 2023

ENGLISH

EORTC QLQ - BR23

Patients sometimes report that they have the following symptoms or problems. Please indicate the extent to which you have experienced these symptoms or problems during the past week.

During the past week:	Not at All	A Little	Quite a Bit	Very Much
31. Did you have a dry mouth?	1	2	3	4
32. Did food and drink taste different than usual?	1	2	3	4
33. Were your eyes painful, irritated or watery?	1	2	3	4
34. Have you lost any hair?	1	2	3	4
35. Answer this question only if you had any hair loss: Were you upset by the loss of your hair?	1	2	3	4
36. Did you feel ill or unwell?	1	2	3	4
37. Did you have hot flushes?	1	2	3	4
38. Did you have headaches?	1	2	3	4
39. Have you felt physically less attractive as a result of your disease or treatment?	1	2	3	4
40. Have you been feeling less feminine as a result of your disease or treatment?	1	2	3	4
41. Did you find it difficult to look at yourself naked?	1	2	3	4
42. Have you been dissatisfied with your body?	1	2	3	4
43. Were you worried about your health in the future?	1	2	3	4
During the past four weeks:	Not at All	A Little	Quite a Bit	Very Much
44. To what extent were you interested in sex?	1	2	3	4
45. To what extent were you sexually active? (with or without intercourse)	1	2	3	4
46. Answer this question only if you have been sexually active: To what extent was sex enjoyable for you?	1	2	3	4

Please go on to the next page

Pre-Operative Window of Adjuvant Endocrine Therapy to Inform Radiation Therapy Decisions in Older Women with Early-Stage Breast Cancer

Version Date: 21 February 2023

ENGLISH

During the past week:	Not at All	A Little	Quite a Bit	Very Much
47. Did you have any pain in your arm or shoulder?	1	2	3	4
48. Did you have a swollen arm or hand?	1	2	3	4
49. Was it difficult to raise your arm or to move it sideways?	1	2	3	4
50. Have you had any pain in the area of your affected breast?	1	2	3	4
51. Was the area of your affected breast swollen?	1	2	3	4
52. Was the area of your affected breast oversensitive?	1	2	3	4
53. Have you had skin problems on or in the area of your affected breast (e.g., itchy, dry, flaky)?	1	2	3	4

Pre-Operative Window of Adjuvant Endocrine Therapy to Inform Radiation Therapy Decisions in Older Women with Early-Stage Breast Cancer

Version Date: 21 February 2023

Appendix 8: Center for Epidemiologic Studies Depression Scale Revised

Below is a list of the ways you might have felt or behaved. Please check the boxes to tell me how often you have felt this way in the past week or so.	LAST WEEK				
	Not at all or Less than 1 day	1-2 days	3-4 days	5-7 days	Nearly every day for 2 weeks
	My appetite was poor.				
I could not shake off the blues.					
I had trouble keeping my mind on what I was doing.					
I felt depressed.					
My sleep was restless.					
I felt sad.					
I could not get going.					
Nothing made me happy.					
I felt like a bad person.					
I lost interest in my usual activities.					
I slept much more than usual.					
I felt like I was moving too slowly.					
I felt fidgety.					
I wished I were dead.					
I wanted to hurt myself.					
I was tired all the time.					
I did not like myself.					
I lost a lot of weight without trying to.					
I had a lot of trouble getting to sleep.					
I could not focus on the important things.					

Pre-Operative Window of Adjuvant Endocrine Therapy to Inform Radiation Therapy Decisions in Older Women with Early-Stage Breast Cancer

Version Date: 21 February 2023

Appendix 9: Breast Cancer Prevention Trial Symptom Checklist

EVERYDAY PROBLEMS DURING THE PAST 4 WEEKS

We are interested in knowing how much you have been bothered by any of the following problems during the **PAST 4 WEEKS**. (Circle one number on each line. If you do not have the problem, circle "not at all".)

During the **past 4 weeks**, how much were you bothered by:

	Not at all	Slightly	Moderately	Quite a bit	Extremely
	0	1	2	3	4

1. Hot flashes.....
2. Nausea.....
3. Vomiting.....
4. Difficulty with bladder control when laughing or crying.....
5. Difficulty with bladder control at other times.....
6. Vaginal dryness.....
7. Pain with intercourse.....
8. General aches and pains.....
9. Joint pains.....
10. Muscle stiffness.....
11. Weight gain.....
12. Unhappy with the appearance of my body.....
13. Forgetfulness.....
14. Night sweats.....
15. Difficulty concentrating.....
16. Easily distracted.....
17. Arm swelling (lymphedema).....
18. Decreased range of motion in arm on surgery side.....

Pre-Operative Window of Adjuvant Endocrine Therapy to Inform Radiation Therapy Decisions in Older Women with Early-Stage Breast Cancer

Version Date: 21 February 2023

Stanton, A. L., Bernaards, C. A., & Ganz, P. A. (2005). The BCPT Symptom Scales: A measure of physical symptoms for women diagnosed with or at risk for breast cancer. Journal of the National Cancer Institute, 97, 448-456.

Pre-Operative Window of Adjuvant Endocrine Therapy to Inform Radiation Therapy Decisions in Older Women
with Early-Stage Breast Cancer

Version Date: 21 February 2023

Appendix 10: Adherence Questions

UVA IRB-HSR 22040: POWER Trial

Health-Related Quality of Life Questionnaires

Adherence Questions

In an average week, how often do you take your hormone treatment for breast cancer? Choose the best answer from the options below? **Note: On Day 1, please mark N/A**

Every Day **Most Days** **Some Days** **Rarely** **I stopped taking it.**
(out of 7 days) (5 out of 7 Days) (3-4 out of 7 Days) (1-2 out of 7 Days)

N/A

At this time, how likely is it that you will complete the entire recommended duration (i.e. 7-10 years) of your hormone treatment for breast cancer?

1

2

3

4

=Extremely Unlikely

=Unlikely

=Likely

=Extremely Like

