8.2.3 Patient Reported Outcome Surveys

Patient reported outcomes will be assessed as indicated in [Appendix 1](#).

Health related quality of life (HRQOL) will be assessed using the EORTC QLQ-C30 and QLQ-BR23 ([Appendix 7](#)), which is a validated and reliable 53 question assessment of general health and wellbeing⁴⁴.

Depression will be assessed using the Center for Epidemiologic Studies Depression Scale Revised (CESD-R, [Appendix 8](#)), which is a 20 item assessment to measure symptoms of depression in nine different groups as defined by the American Psychiatric Association Diagnostic and Statistical Manual, fifth edition. The score ranges from 0 to 60 and scores greater than 16 indicate depressive symptoms⁴⁵.

Pre-Operative Window of Adjuvant Endocrine Therapy to Inform Radiation Therapy Decisions in Older Women with Early-Stage Breast Cancer

Version Date: 21 February 2023

General symptom burden while on endocrine therapy will be assessed using the Breast Cancer Prevention Trial Symptom Checklist (BCPT-SCL, [Appendix 9](#)) in which 47 symptoms are assessed on a scale of 0 to 4 (high burden) with plans to follow symptom clusters used in the ELPh trial of weight/body image, vasomotor, vulvovaginal, musculoskeletal, cognitive, and mood^{33,46,47}.

Data will be collected on patient adherence to endocrine therapy using patient report via two simple questions ([Appendix 10](#)).

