10.3 Sample Size Determination

Sample size estimation is based upon accruing a sufficient number of participants to assess the primary objective separately for participants and surgical oncologist responses with an overall one-sided 10% type I error rate (5% for each individual test). Accrual of 70 evaluable participants provides 90% power to test for a change in adjuvant radiation treatment preference between the pre-op visit and on-study in the participant study population from a null difference of 5% to an alternative of at least 15% with a target one-sided 5% level binomial test (by exact enumeration). Accrual of 70 evaluable participants also provides 90% power to independently test for a change

Pre-Operative Window of Adjuvant Endocrine Therapy to Inform Radiation Therapy Decisions in Older Women with Early-Stage Breast Cancer

Version Date: 21 February 2023

in adjuvant radiation treatment preference of the surgical oncologist between the pre-op visit and on-study in the participant study population from a null difference of 5% to an alternative of at least 15% with a one-sided 5% level binomial test. For fixed target size and power, the detectable difference increases from 10% to 15% when the assumed null varies within the expected range of 5% to 20%.

This is a pilot study to obtain preliminary data to estimate which if any PRO measures are associated with adherence to post-operative endocrine therapy. With n=70, a logistic regression of the dependent variable of adherence or not to endocrine therapy by year 2 on a continuous PRO measure score achieves 80% power at a 5% significance level to detect an odds ratio of 2 when the probability of adherence is 25%. These error rate estimates assume no adjustment for multiple comparisons among the different PRO.

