10.4 Accrual

Maximum target sample size is estimated at 83 eligible participants which adjusts for a 15% lost to follow-up/dropout rate. In 2018 and 2017, 70 and 78 patients, respectively, met the basic inclusion criteria at UVA. Assuming 60% of future patients will agree to enroll in the study, target accrual to the study should be achieved in less than two years.

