10.5.2 Analyses

Primary analyses will not adjust for center. Summary measures will be described overall and by center. Demographics and baseline characteristics will be described for all study participants. Characteristics to be examined include: race/ethnicity, age, performance status, stage, ER, PR and HER-2 status, histologic subtype, tumor size date of diagnosis.

Adverse events will be coded based upon the NCI CTCAE v5.0. Safety will be reported by frequency and severity of adverse events.

The primary analysis will be based upon responses from a) study participants and b) surgical oncologists to the radiation questions, separately, without adjustment for center. For each response group, the proportion of responses that differ from the pre-op visit compared to the on-study (baseline) response (yes to no; or no to yes) will be calculated along with 95% confidence intervals. For each group, we will test that pre-ET resulted in a change in preference for adjuvant

Pre-Operative Window of Adjuvant Endocrine Therapy to Inform Radiation Therapy Decisions in Older Women with Early-Stage Breast Cancer

Version Date: 21 February 2023

radiation therapy in more than 10% of participants compared to no change with a one-sided 5% level exact binomial test.

Graphical methods will be used to display the PRO outcomes over time. On the most basic level, logistic regression models with adherence to post-op endocrine therapy at 2 years as the dependent outcome and the range of PRO measurement as independent factors will be used to obtain initial estimates of the predictive value of the protocol defined PRO to determine adherence. Other exploratory repeated measures models will be explored to determine if changes over time are also associated with determination of non-adherence. Exploratory analyses could include the assessment of PRO for quality adjusted life years or healthy-year equivalents. In all exploratory models, individual or simultaneous associations will be deemed promising for factors with $p < 0.1$.

The secondary analysis related to the radiation oncologist's preference will be based upon the subset of pre and post pre-ET responses from for the consulting radiation oncologist. The proportion of responses that differ from the pre-op visit compared to the on-study (baseline) response by at least one point (in either direction) will be calculated along with a 95% confidence interval.

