10.5.3 Interim Analyses and Pausing Guidelines

There will be no planned interim analyses for testing the primary hypotheses. Participants will be monitored for adherence to pre-ET and for pre/post response data capture. Pre-operative ET treatment adherence is expected to be close to 100% thus an indication of a lower rate would be cause for pause. After accrual of 50% of eligible participants, if the upper limit of a 90% CI around the adherence rate does not contain 80% then the study will be paused to assess the cause, which may result in no modification, study modification or closure. Similarly, the study will be monitored for any indication that use of 3 months of pre-ET negatively impacts surgical completion with the same decision guideline.

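### The adherence item in Appendix 10 has no box whose number covers 6 of 7 days, which matters for the 2-year outcome only if the unstated adherence cut falls between Every Day and Most Days

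*Combined protocol and SAP*

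**What the plan says.** Section 8.2.3 names the source of the adherence data: "Data will be collected on patient adherence to endocrine therapy using patient report via two simple questions". Sections 4.1 and 6.4 also rely on patient report. The questions are in Appendix 10. The first asks how often the drug is taken in an average week, and the second asks how likely the woman is to complete the full course. Only the first concerns how regularly doses are taken.

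The boxes of the first question are *Every Day*, then "Most Days Some Days Rarely I stopped taking it", then N/A. The brackets under the first four read "out of 7 days) (5 out of 7 Days) (3-4 out of 7 Days) (1-2 out of 7 Days". The instruction is "Choose the best answer from the options below".

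The answer feeds the secondary objective. Section 10.5.2 plans "logistic regression models with adherence to post-op endocrine therapy at 2 years as the dependent outcome". For that model section 10.3 states that 70 women "achieves 80% power at a 5% significance level to detect an odds ratio of 2 when the probability of adherence is 25" per cent. No section says which boxes count as adherent.

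Section 10.5.3 separately provides for a pause "if the upper limit of a 90% CI around the adherence rate does not contain 80" per cent. It does not say how a woman is classed as adherent for that rate.

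**The concern.** A frequency item should give every possible answer one box. Here the two lower bands are ranges that meet without a gap, but *Most Days* carries one number, 5. A woman who misses one dose a week fits *Most Days* in words but not by its number, and *Every Day* in neither. Women with the same behaviour can therefore be recorded in different boxes.

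If adherent is later defined as *Every Day*, that inconsistency lies on the line between adherent and non-adherent. Some non-adherent women would be counted as adherent, which weakens the estimated association between PRO scores and adherence and removes events from a small sample. A dose threshold strictly between 5/7 and 7/7 could not be applied to the form at all. What a visit did not record cannot be recovered at analysis.

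**Working it through.** **1. Coverage of the boxes.** Read *Every Day* as 7 and the stopped box as 0. The boxes then cover 7; 5; 3-4; 1-2; 0. Of the whole-day values 0 to 7, only 6 is missing. As shares of doses: 6/7 = 85.7%, against 7/7 = 100% and 5/7 = 71.4% for the neighbouring boxes.

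**2. The plan's own figures.** From sections 10.3 and 10.4: n = 70, OR 2, probability 25%, 5% level, 80% power, 15% dropout. The unit of the OR is not stated; one SD of the PRO score is assumed. The usual formula for one continuous covariate is n = (z_α + z_β)² / [p(1−p)(ln OR)²].

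- One-sided 5%: (1.645 + 0.842)² / [0.25 × 0.75 × 0.693²] = 68.6, so 69. Power at 70 is 80.7%.
- Two-sided 5%: 87.1, so 88. Power at 70 is 70.9%.

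The stated 80% reproduces with a one-sided test; section 10.3 does not give the sidedness for this model. For dropout, 70/0.85 = 82.4, so 83, which matches section 10.4.

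**3. Number of women concerned.** The documents give no frequency for a 6-of-7 pattern. If it were 5%, 10% or 20% of 70, that is 3.5, 7 or 14 women.

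**4. Effect on the 2-year outcome if the cut is below *Most Days*.** Both neighbouring boxes count as adherent, so the outcome does not change.

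**5. Effect if only *Every Day* counts as adherent.** Every 6-of-7 woman is then truly non-adherent, and the only possible error is that she is recorded as adherent. Assume 25% truly non-adherent, 10% or 20% of all women at 6 of 7 days, and half of these ticking *Every Day*. Section 10.3 gives 25% as the probability of adherence. The formula in step 2 is the same for p and 1−p, but the simulated figures below hold for 25% non-adherent.

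- Truly non-adherent: 0.25 × 70 = 17.5.
- At 10%: 7 women, 3.5 misrecorded, 14 events left.
- At 20%: 14 women, 7 misrecorded, 10.5 events left.

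Simulated logistic regression (n = 70, OR 2 per SD):

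| Share at 6 of 7 days | Median OR | Power at p<0.1 |
|---|---|---|
| 0% | 2.04 | 74% |
| 10% | 1.94 | 64% |
| 20% | 1.80 | 49% |

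A second run of the same model gave 1.94 and 1.82 for the OR and 63% and 50% for power, so the figures are good to about one or two units in the last digit. The p<0.1 level is the one that section 10.5.2 uses to call a factor promising. The simulated starting power of 74% is below the 80.7% of the approximate formula, so compare rows within the table only.

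**6. Pausing guideline.** Half of 83 is about 41 women. The upper 90% limit first falls below 80% at 27 of 41 adherent (limit 0.780, exact and normal approximation alike), that is, at 14 failures. At 10-20%, about 4-8 of the 41 women would lack an exact box.

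**The case against.** The case on the other side is substantial, and much of it stands.

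- **The wording helps the woman.** She is asked for the best answer, and in ordinary English *Most Days* takes in 6 of 7 days while *Every Day* does not. Only the bracketed 5 conflicts. The even split between the two boxes is therefore an assumption without support, and the true share ticking *Every Day* may be well below half.
- **Text may have been lost.** The first bracket has no numeral before its words, and the last answer of the second question ends in a truncated word. A dropped upper bound on *Most Days* cannot be excluded, although the ranges in the next two brackets came through intact. The form in use must be checked before the gap is treated as real.
- **The 20% case is extreme.** It makes 14 of 17.5, or four-fifths, of all non-adherent women 6-of-7 takers.
- **The outcome is a preliminary secondary estimate in a pilot.** No primary result depends on it.

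A reader might go further in four ways that the documents do not support. First, that this is the most common mild lapse: no frequency of any missed-dose pattern is given. Second, that the answer is scored as full or as 5-of-7 adherence: no scoring rule exists, so one can say only how it is recorded. Third, that the error is random in both directions. Replacing the outcome by a coin flip in 10% or 20% of all women gives median ORs of 1.82 and 1.62, but this creates false non-adherent women, which an *Every Day* cut cannot produce. The pull toward 1 is smaller, though the power loss is similar. Fourth, that the gap shifts the pausing rule. Section 10.5.3 does not name this item as its source. Section 8.1.1 records start and stop dates, and section 6.2.1 allows for women who stop pre-operative therapy before 90 days. Either could define adherence there. The link is possible but not stated, and 4-8 women could not by themselves reach 14 failures.

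What remains is the gap at 6 days as printed, on the only question about how regularly doses are taken. Start and stop dates show persistence, not missed doses.

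**Conclusion.** As printed, the item leaves 6 of 7 days without a matching number, so equal behaviour can be recorded unequally. Whether this reaches the 2-year outcome depends on a cut that section 10 does not give, and that omission is the larger gap. If *Most Days* counts as adherent, the effect is nil. If only *Every Day* counts, and if 10-20% of women are at 6 of 7 days with half of them ticking *Every Day*, the median OR drops from about 2.04 to 1.94-1.80 and power at p<0.1 from about 74% to 64-49%. Those figures also rest on an OR of 2 per SD and 25% truly non-adherent.

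The stated sample size, power and dropout figures stand. The point is a minor improvement to data collection, conditional on the form in use matching the printed appendix.

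**What to change.** 1. Check the form given to participants for text missing from the brackets. If *Most Days* already includes 6, correct the appendix only.
2. If the gap is real, print *Every Day (7 out of 7 Days)* and *Most Days (5-6 out of 7 Days)* at the next amendment, and record the form version with each answer.
3. State in section 10 which boxes count as adherent at 2 years.
4. For answers on the old form, run one sensitivity analysis with the cut on the other side of *Most Days*.

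The cost is a one-line form change, a version flag, a sentence in section 10 and one additional model. The amendment history shows that these questions have been updated before. The downside is that old and new forms differ slightly in one category, which the version flag and the sensitivity analysis address.
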